5 DEFINITIONS

5.1 Baseline

Two baselines are defined for the statistical analysis variable derivations.

- **Current study baseline** is defined as the last observed value before the first dosing of the study drug for CL302.
- **Parent study baseline** is defined as the last observed value before the first dosing of the IP study drug from CL202, CL203, or CL301 depending on which study the subject was enrolled from.

Current study baseline is defined for all safety summaries and analyses.

Efficacy summaries and analyses will be performed upon the parent study baseline and the current study baseline as specified in [Table 8.1.1](#).

5.2 Subgroup

The following subgroups are defined for this study:

- Gender (Male and Female)
- Age (above and below median)
- Ethnicity (small groups may be combined)
- Genetic Mutation
 - Genotype: Homozygote, Heterozygote, and Compound Heterozygote
 - Mutation type: Exon and Intron

Genetic mutation subgroup analysis will be done for the following primary efficacy endpoints: the changes from baseline in UEC score in subjects enrolled from CL301 and CL202; and the changes from baseline in lower extremity muscle strength of knee extensors in subjects enrolled from CL203.

Gender, age, and ethnicity subgroup summaries will be done to support the safety.

6 ANALYSIS SETS

Three analysis sets are defined for the study.

Full Analysis Set: The full analysis set will include all subjects with a CL302 baseline measurement and at least one post-baseline measurement in CL302. This set will be used for the efficacy analysis.

Safety Analysis Set: The safety analysis set consists of all subjects who receive at least one dose of study drug in CL302. This set will be used for safety analysis.

Sialic Acid Analysis Set: The SA analysis set will consist of all subjects with evaluable free serum SA levels in CL302.

7 DATA SCREENING AND ACCEPTANCE

7.1 General Principles

Data will be reviewed periodically. And any questionable data will be reported to the clinical data manager promptly for query and resolution.

7.2 Handling of Missing and Incomplete Data

Missing clinical outcome data can occur for multiple reasons, including missed subject visits and scales or measures with missing item scores. Missing and incomplete data will be identified through the data quality review plan for this study. Missing and incomplete data will be identified for investigation, and possible resolution, by Data Management prior to the study database lock or snapshot. Unless specified otherwise, only the observed data (not imputed data) will be presented in listings.

7.2.1 Missing Date of the Last Dose of Investigational Product

When the date of the last dose of investigational product is found missing for a subject, all efforts should be made to obtain the date from the Investigator. If after all efforts are made it is still missing, the last dosing visit date will be used as the last dose date.

7.2.2 Missing Efficacy Data

Details of missing HHD observations for individual muscle groups and individual questions for GNEM-FAS are provided in Appendix 10.2.

7.2.3 Missing Dates Information for Adverse Events and Concomitant Medications

The following conventions will be used to impute missing portions of dates for adverse events and concomitant medications. Note that the imputed values outlined here may not always provide the most conservative date. In those circumstances, the imputed value may be replaced by a date that will lead to a more conservative analysis.

Missing Start Dates

- If the day is unknown, then:
 - If the month and year match the first dose of investigational product start date month and year in this study, then impute the day of the first dose date.
 - Otherwise, assign the first day of the month.
- If the month is unknown, then:
 - If the year matches the year of the first dose of investigational product date in this study, then impute the month and day of the first dose date in this study.
 - Otherwise, assign ‘January’

- If the year is unknown, then the date will not be imputed and will be assigned a missing value.

If the imputed date is earlier than birth date, then birth date will be used

Missing Stop Dates

- If the day is unknown, then assign the last day of the month.
- If the month is unknown, then assign ‘December.’
- If the year is unknown, then the date will not be imputed and will be assigned a missing value.

If the resulting end date is after the date of study completion / discontinuation/ data cutoff, set the imputed end date as the date of study completion / discontinuation/ data cutoff.

7.2.4 Missing Causal Relationship to Investigational Product for Adverse Events

If the causal relationship to the investigational product is missing for an AE that started on or after the date of the first dose of investigational product, a causality of “definitely related” will be assigned. The imputed values for causal relationship to investigational product will be used for the incidence summary; the values will be shown as missing in the data listings.

7.2.5 Visit Time Windows

There is no visit time window applied to handle the missing values for a scheduled visit. Nominal visits will be used for by-visit analyses. If an unscheduled visit has to be used, the principle of proximity will be applied.

7.3 Handling of Multiple Measurements in HHD

Each muscle strength is assessed three times in Hand Held Dynamometry (HHD) measurement. The highest value of the three will be used for summary and derivation of efficacy endpoints.

7.4 Testing/Validation Plan

Data will be reviewed by cross functional team periodically and issues will be addressed by clinical data management.

7.5 Software

SAS® software version 9.2 or higher will be used to perform statistical analyses unless otherwise specified.

8 STATISTICAL METHODS OF ANALYSES

8.1 General Principles

All statistical tests will be two-sided and a difference resulting in a p-value of less than or equal to 0.05 will be considered statistically significant. All p-values will be rounded to and displayed in four decimals. If a p-value less than 0.0001 occurs, it will be shown in the table as <0.0001.

Continuous variables will be summarized by number of subjects and mean, SD/SE, median, minimum, and maximum values. Categorical variables will be summarized by number and percentage. No imputation on missing data will be made, unless stated otherwise.

Data collected will be presented in listings. Data not subject to analysis according to this plan will not appear in any tables or graphs but will be included in the data listings.

Post-hoc exploratory analyses not identified in this SAP may be performed to further examine the study data. These analyses will be clearly identified as such in the final clinical study report. The SAP will not be amended for post-hoc or additional analyses identified after planned analyses are completed. Similarly, additional tables and figures may be defined to further evaluate study results and the SAP will not be amended to list them.

Efficacy analyses will be presented by the parent study as illustrated in [Table 8.1.1](#): UX001-CL301, CL202 or CL203. Different efficacy endpoints at different scheduled time points were collected depending on which parent study the subjects were enrolled from.

Safety analyses will be presented by the parent studies and overall as illustrated in [Table 8.1.1](#). Subjects enrolling from UX001-CL301 will be further examined by the treatment group assigned in the parent study: placebo, Ace-ER 6 g/day, and All.

[Table 8.1.1](#) also provides the guidance for the treatment groups to be displayed for biomarker analyses as well as efficacy analyses and safety analyses, which have been described above. Baseline used for the analyses are specified as well. Example table templates are provided in [Appendix 10.6](#) for efficacy and safety.

Table 8.1.1: Analysis Presentation

Analysis Category	Analysis Set	Parent Study	Treatment Group	Baseline Applied	
Week 96/ET efficacy analysis	Full Analysis Set	CL301	Placebo*	Parent Study Baseline	
			Ace-ER 6 g/day		
			Placebo*	Current Study Baseline	
			ACE-ER 6 g/day		
			All		
Week 96/ET efficacy analysis	Full Analysis Set	CL202	Ace-ER 6 g/day	Current Study Baseline	
Week 96 /ET efficacy analysis	Full Analysis Set	CL203	Ace-ER 6 g/day	Parent Study Baseline	
			Ace-ER 6 g/day	Current Study Baseline	
Week 96/ET safety analysis	Safety Analysis Set	CL301	Placebo*	Current Study Baseline	
			Ace-ER 6 g/day		
			All		
		CL202	Ace-ER 6 g/day		
		CL203			
		Total			
Week 96/ET analysis on biomarkers	Sialic Acid Analysis Set	CL301	Ace-ER 6 g/day	Current Study Baseline	
		CL202			
		CL203			
		Total			

* This refers to the enrolled subjects who had received placebo treatment in parent study CL301.

8.2 Subject Disposition

All subjects screened for the study will be used for reporting of disposition. Subject disposition summaries will include the number and percentage of subjects who are included in the safety, efficacy, and SA analysis sets; the number and percentage of subjects who received study drug treatment, completed the study or discontinued the study (with reasons) will be summarized by parent study and total.

8.3 Protocol Deviations

Major protocol deviations will be summarized. All protocol deviations will be listed.

8.4 Demographic and Baseline Characteristics

Demographic and baseline characteristics will be summarized descriptively for the full analysis set.

- Gender
- Age
- Age at start of parent study
- Race
- Ethnicity
- Height (cm)
- Weight (kg)
- Genotype: Homozygote, Heterozygote, and Compound Heterozygote
- Mutation type: Exon and Intron

8.5 Investigational Product Administration

8.5.1 Extent of Exposure

The total number of doses administered, the total dose administered, and the total treatment duration will be summarized for the Safety Analysis Set. The calculation will be based on the current study baseline unless otherwise specified.

Study medication dispensing and treatment compliance will also be listed.

8.5.2 Measurement of Treatment Compliance

Dosing compliance for a CL302 study period is defined as:

$$\frac{\text{Actual total dosage taken during CL302}}{\text{Planned dosage for CL302}} * 100\%$$

Descriptive statistics will be reported for compliance on the Safety Analysis Set.

8.6 Efficacy Analysis

Efficacy analyses will use generalized estimating equation (GEE) (Hanley et al. 2003) to evaluate trends over time with respect to the changes from baseline for all continuous efficacy endpoints. Baseline will be included as a covariate in the model. GEE will be the primary analysis method for all repeated measures endpoints. The statistical analyses will be reported in summary tables, figures, and data listings. Statistical tests will be 2-sided at the alpha=0.05 significance level.

Efficacy analysis will be based on the full analysis set.

Additional efficacy analyses may be performed for subjects enrolled in CL301 by incorporating data from both the parent study and the current study to compare the placebo versus UX001 treatment groups using the methodology described in ([Hu et al. 2007](#)). Such analyses examine the extended treatment effect of UX001 on the placebo subjects who now are taking UX001 in the extension study.

Parent study baseline will be used to evaluate the long-term study drug effect from the parent study drug administration, except for subjects enrolling from CL202.

Current study baseline will be used to evaluate the continuous long-term study drug effect going on after the parent study.

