### 7.6.1 Determination of Sample Size

The current study is primarily designed to evaluate safety and the sample size is intended to provide the maximum amount of information regarding UX001 tolerability along with indicators of long-term safety and efficacy in this patient population. Approximately 165 adult subjects with GNEM are expected to roll-over from UX001-CL202 (N=55), UX001-CL301 (N=80), and UX001-CL203 (N=30) studies to participate in this extension study.

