### 7.6.4 Efficacy Analysis

Separate analyses will be performed for subjects coming from each parent study.

The full analysis set will include all subjects with a baseline measurement and at least one post-baseline measurement. This set will be used for the analyses of all efficacy endpoints.

Baseline values for each endpoint will be defined as the last scheduled data collection visit before first dose according to the Schedule of Events ([Table 2.1](#)).

Efficacy analyses will use generalized estimating equation (GEE) to evaluate trends over time with respect the changes from baseline for the primary efficacy endpoint, and all secondary and tertiary efficacy endpoints. Baseline will be included as a covariate in the model. This method will be the primary analysis method for all repeated measures endpoints.

The statistical analyses will be reported using summary tables, figures, and data listings.

Statistical tests will be 2-sided at the alpha=0.05 significance level.

Continuous variables will be summarized with means, standard deviations, medians, minimums, and maximums. Categorical variables will be summarized by counts and by percentages of subjects in corresponding categories.

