3.5 Sample Size Considerations

The current study is primarily designed to evaluate safety and the sample size is intended to provide the maximum amount of information regarding UX001 tolerability along with indicators of long-term safety and efficacy in this patient population. Approximately 180 adult subjects with GNEM are expected to roll-over from UX001-CL202, UX001-CL301, and UX001-CL203 studies to participate in this extension study.

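### GEE for the CL203 cohort (about 30 subjects) has no stated variance estimator or small-sample correction; with the usual uncorrected robust variance, nominal 5% tests would run at about 6% to 7%

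*SAP*

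**What the plan says.** SAP 8.6 sets the method: "GEE will be the primary analysis method for all repeated measures endpoints". It adds "Baseline will be included as a covariate in the model" and "Statistical tests will be 2-sided at the alpha=0.05 significance level".

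Protocol 7.6.4 keeps the cohorts apart: "Separate analyses will be performed for subjects coming from each parent study". Protocol 7.6.1 expects them to come from "UX001-CL202 (N=55), UX001-CL301 (N=80), and UX001-CL203 (N=30) studies". SAP 3.5 raises the total without a split: "Approximately 180 adult subjects with GNEM are expected to roll-over from UX001-CL202, UX001-CL301, and UX001-CL203 studies".

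SAP Appendix 10.1 assigns a GEE model to all CL203 primary efficacy endpoints at Weeks 24, 48, 72 and 96. It assigns summary statistics to the tertiary endpoints and to the CL203 exploratory endpoints.

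SAP 5.2 plans a genetic subgroup analysis of knee extensor strength in CL203 and of UEC in CL202 and CL301. One grouping is "Genotype: Homozygote, Heterozygote, and Compound Heterozygote"; the other is mutation type. SAP 5.2 gives no class counts and names no model.

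Protocol 7.6 leaves the detailed method for each variable to the SAP. The SAP gives a SAS version (7.5) but no variance estimator, working correlation, reference distribution or small-sample correction.

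**The concern.** The usual GEE inference divides the estimate by a robust (sandwich) standard error and refers the ratio to the normal distribution. Both steps rely on many independent subjects. With few, the sandwich variance is too small on average, because residuals understate the errors, and the normal reference ignores the uncertainty in that variance. Both errors make p-values too small and intervals too narrow.

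CL203 is the smallest cohort and stands alone. SAP 4.2 lists as primary for it four GNEM-FAS Expanded scores, plus strength and percent predicted for five muscle groups: 4 + 5 × 2 = 14 endpoints. SAP Table 8.1.1 applies two baselines, giving 14 × 2 = 28 GEE analyses. Genotype classes within the cohort would be smaller still. At stake is whether the 0.05 threshold and the intervals in these efficacy analyses have their stated meaning.

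**Working it through.** **Inputs from the documents.** Two-sided alpha 0.05 and baseline as covariate (SAP 8.6); 30 CL203 subjects (Protocol 7.6.1); four post-baseline visits (SAP Table 4.2.1 and Appendix 10.1).

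**The plan's own figure.** 55 + 80 + 30 = 165, as the protocol states. The SAP's 180 has no split; pro rata, CL203 would be 30 × 180/165 ≈ 33, which changes little. The documents give no power or actual error rate to reproduce.

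**Assumptions.** Uncorrected sandwich variance with a normal reference; no true change; normally distributed outcomes. Genotype class sizes are assumptions. An equal three-way split gives 30/3 = 10 in CL203, 55/3 ≈ 18 in CL202 and 80/3 ≈ 27 in CL301. A class of 6 represents an uneven split.

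**Closed form for a mean.** The uncorrected sandwich variance is ((n-1)/n) × s²/n, so the actual size is 2 × P(t with n-1 df > 1.96 × √((n-1)/n)). For n = 30, 1.96 × √(29/30) = 1.927, and the two-sided tail on 29 df is 6.4%.

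**Simulation.** Four visits, baseline covariate, independence working correlation, exchangeable true correlation of 0.5 or 0.8, 40,000 trials per setting for n = 30 and n = 10. The n = 18 and 27 rows are 6,000-trial slope runs. The n = 6 row comes from 6,000-trial runs that also covered other correlation structures, with a visit-mean contrast in the last column.

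| n | Closed form | Slope | Week 96 mean |
|---|---|---|---|
| 30 | 6.4% | 6.4% to 6.5% | 6.6% to 6.8% |
| 27 | about 6.5% | 6.4% to 6.8% | not run |
| 18 | 7.4% | 7.2% to 7.3% | not run |
| 10 | 9.6% | 9.4% to 9.7% | 10.8% to 11.5% |
| 6 | 13.4% | 12.8% to 13.3% | 15.1% to 17.3% |

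A cross-check with a standard GEE routine, with 0% and 20% dropout and 1,500 trials per setting, gave 5.9% to 7.7% at n = 30 and 8.3% to 10.0% at n = 10.

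**Interval width.** The mean sandwich standard error was 0.96 to 0.97 of the true value at n = 30, a shortfall of 3% to 4%. At n = 10 the ratio was 0.87 to 0.92. The normal reference adds to this: at n = 30, 1.960/2.048 (t on 28 df) = 0.957.

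**Fewer than 30 for knee extensors.** The protocol synopsis tests only subjects who can be positioned, and SAP 10.2 leaves bilateral too-strong readings missing. At n = 25 the simulated size was 6.5% to 7.1%.

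**Corrected methods.**
- Kauermann-Carroll with t on n-2 df: 4.7% to 5.4% at n = 30, 15 and 10. A repeat with 20,000 trials per setting (exchangeable correlation 0.6) gave 4.3% to 5.3% over n = 10, 18, 27 and 30.
- Mancl-DeRouen with t on n-2 df: 4.3% to 4.7% at n = 30, but 3.3% to 3.7% at n = 10, which is conservative.

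**The case against.** The strongest reply is that the SAP never chooses the uncorrected sandwich. A reader might infer that it does, but the text is silent, and the result depends on the choice. Model-based standard errors, under an exchangeable working correlation that matched the simulated truth, gave 6.2% at n = 30 and 3.4% to 4.6% at n = 10. This stands: the error rate is conditional on an estimator that the plan does not name. It does not remove the point. Model-based errors under an independence working correlation gave 0.5% to 0.8% at n = 30 in the same cross-check, so the unstated choice decides whether the test is liberal or very conservative.

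A reader might also infer that GEE will be run in genotype classes of about 10, at error rates near 11%. The documents do not support that as fact. SAP 5.2 names no model, Appendix 10.1 has no subgroup row, and the knee extensor table template in Appendix 10.7 shows only descriptive statistics. GEE within classes is implied by SAP 8.6 and no more. An equal split is also doubtful: Protocol 5.1 describes the disease as autosomal recessive, so the heterozygote class may be small or empty. The larger cohorts' classes would show much less inflation.

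Nor does every repeated endpoint get a GEE test. The broad wording of SAP 8.6 conflicts with the summary statistics assigned in Appendix 10.1, and the two need reconciling.

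Finally, the study is single-arm, open-label and designed primarily for safety, so little hangs on these p-values. That limits the importance of the point but does not make the intervals right.

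**Conclusion.** The point holds in a limited form. GEE is the primary method for all CL203 primary efficacy endpoints, in a separately analysed cohort of about 30, and the plan does not say how its standard errors and p-values will be obtained. Under the usual default the excess error at n = 30 is 1 to 2 percentage points. This is modest, and always towards overstating the evidence.

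The larger figures, up to 9% to 11% at n = 10 and 13% or more at n = 6, apply only if GEE is run within genotype classes and the classes are that small. The documents settle neither.

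A reader might conclude that the study's main conclusions are unsafe. They are not affected: the primary objective is safety, reported descriptively, and only efficacy p-values and intervals are involved. A better method costs little, so the SAP should be changed.

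**What to change.** In SAP 8.6, state the working correlation, variance estimator and reference distribution. For CL203 and for any GEE within genotype subgroups, specify the Kauermann-Carroll bias-corrected robust variance with a t reference on about N-2 degrees of freedom. An acceptable alternative is REML repeated measures with Kenward-Roger degrees of freedom. Mancl-DeRouen with t is usable at 30 but conservative near 10, so the two corrections should not be treated as interchangeable.

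In SAP 5.2, state whether the genetic subgroup analysis is model-based, and keep it descriptive where classes are very small. Align SAP 8.6 with Appendix 10.1 on which endpoints receive GEE.

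The cost is a few SAP sentences and a software option or short program, with no change to data collection or conduct. Intervals widen: at n = 30, replacing 1.960 by 2.048 adds about 4.5%, and removing the 3% to 4% shortfall in the standard error brings the total to roughly 8% (1.045/0.97 = 1.077; 1.045/0.96 = 1.089).

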8.7 Safety Analysis

The safety analysis will be performed on the safety analysis set. Descriptive statistics will be provided for safety reporting by parent study and overall.

8.7.1 Adverse Events

All AEs recorded from the time the subject signs the informed consent through the safety follow-up will be coded using the Medical Dictionary for Regulatory Activities (MedDRA version 17.1 or beyond).

The following AEs were collected:

- All AEs;
- All SAEs;
- Treatment-related AEs;
- Treatment-related SAEs;
- AEs leading to the discontinuation of study drug or discontinuation of study;
- Deaths.

The number and proportion of subjects with any treatment-emergent adverse events (TEAEs) (defined generally as any AE started on or after the first dose of study drug) will be summarized by System Organ Class (SOC), Preferred Term (PT), severity, grade, outcome and relationship to treatment for the following types of AEs. Additional summaries of subject incidence (by preferred term) will also be provided.

An AE continued from the parent study would be excluded since they were summarized in the parent study. However, if an AE continued from the parent study and the severity changed to worse will be considered as a TEAE and be summarized.

The severity of AEs will be based on Common Terminology Criteria for Adverse Events (CTCAE), Version 4.03. If an AE cannot be graded based on CTCAE, the investigator will assign a severity based on 1 = mild, 2 = moderate, 3 = severe, 4 = life threatening, and 5 = Death.

For those AEs that occurred more than once during the study, the maximum severity or highest grade will be used to summarize the subject incidence.

Detailed listings for all AEs, serious AEs, AEs leading to the discontinuation of study, and death will also be provided.

Subgroup analyses by gender, age (above and below median), and ethnicity (small group may be combined) will be performed to support the safety in GNEM patients.

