#### **5.2.4 Summary of Overall Risks and Potential Benefits**

GNEM is a rare and severely debilitating disease of adult onset myopathy and progressive muscle weakness with no currently approved therapy and significant unmet medical need. Strong pre-clinical evidence demonstrated that direct substrate replacement therapy may be a promising therapeutic approach for patients with GNEM. Aceneuramic acid is chemically identical to the endogenous monosaccharide sialic acid and its extended release formulation leads to stable improvement of SA levels.

Aceneuramic acid at a dose of 6 g/day has demonstrated positive pharmacodynamic effects such as increasing tissue and serum SA levels as well as lowering of serum creatine kinase

(CK) levels that support the clinical efficacy observed in a randomized, double-blind, placebo-controlled study. The clinical efficacy data at 6 g/day demonstrates muscle strength stabilization and preservation of functional independence relative to placebo or lower dose treatment. Safety information collected over approximately 2.5 years demonstrates that aceneuramic acid has a favorable safety profile.

Each clinical study assessed AEs and SAEs at every scheduled study visit from the time of informed consent. As expected with a substrate replacement therapy, Ace-ER has been well tolerated in clinical studies to date. Levels of free SA in serum during 6 g/day administration were only 2 fold greater than in healthy volunteers. There have been no treatment-related serious adverse events and only one withdrawal due to an adverse event over the 2.5 years of observation. Acceptable tolerability has also been demonstrated by a high treatment compliance rate as well by the fact that all subjects who completed the pivotal study elected to participate in the extension study. The incidence of adverse events of gastrointestinal (GI) disturbance including flatulence, dyspepsia, and diarrhoea were greater in the treatment groups than placebo during the first 24 weeks of the pivotal study. Exposure adjusted rates of these GI events were similar when comparing 6 g/day to placebo. Mildly elevated transaminases occurred but were considered most likely related to the underlying skeletal muscle disease rather than to liver injury.

Ace-ER treatment at 6 g/day clearly has a positive benefit-risk profile that supports the proposed indication of treatment of adult patients with GNEM, and has the potential to impact an unmet medical need for GNEM patients.

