### 7.3.3 Removal of Subjects from Therapy or Assessment

In accordance with the Declaration of Helsinki, subjects have the right to withdraw from the study at any time for any reason. The Investigator and Ultragenyx also have the right to remove subjects from the study. Ultragenyx must be notified of all subject withdrawals as soon as possible. Ultragenyx also reserves the right to discontinue the study at any time for either clinical or administrative reasons and to discontinue participation of an individual subject or Investigator due to poor enrollment or noncompliance, as applicable.

Subjects may be removed from the study for the following reasons:

- Occurrence of an unacceptable adverse event (AE)
- A condition or illness that, in the judgment of the Investigator or Ultragenyx, might place the subject at risk or invalidate the study
- At the request of the subject, Investigator, or Ultragenyx, for administrative or other reasons
- Protocol deviation or unreliable behavior

If the reason for removal of a subject from the study is an AE, the AE and any related test or procedure results will be recorded in the source documents and transcribed onto the case report form (CRF). Each clinically significant abnormal laboratory value or other clinically meaningful abnormality should be followed until the abnormality resolves or until a decision is made that it is not likely to resolve. If such abnormalities do not return to normal within 30 days after the last dose given, their etiology should be identified and Ultragenyx should be notified. All unscheduled tests must be reported to Ultragenyx immediately.

If a subject discontinues from the study prematurely, every reasonable effort should be made to perform the Early Termination Visit procedures within four weeks of discontinuation.

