#### **7.6.6 Safety Analyses**

Safety will be evaluated for the overall study population as well as for subjects from the UX001-CL202, UX001-CL301, and UX001-CL203 study.

The safety analysis set will be used for the analyses of all safety endpoints. Safety will be evaluated by the incidence, frequency and severity of AEs and SAEs, and clinically significant changes from study baseline to scheduled time points in:

- Interval history
- Vital signs
- Physical examination findings
- Clinical laboratory evaluations
- Suicidal ideation and behavior assessments (C-SSRS)
- Concomitant medications

All AEs will be coded using the Medical Dictionary for Regulatory Activities (MedDRA). The incidence and frequency of AEs will be summarized by System Organ Class (SOC), Preferred Term (PT), severity, and relationship to treatment. The numbers (frequency) and incidence rates of AEs and SAEs will be summarized by treatment group. A by-subject listing will be provided for those subjects who experience a SAE, including death, or experience an AE associated with early withdrawal from the study or study drug treatment.

Clinical laboratory data will be summarized by the type of laboratory test. The frequency and percentage of subjects who experience abnormal clinical laboratory results (i.e. outside of reference ranges) and/or clinically significant abnormalities will be presented for each clinical laboratory measurement. For each clinical laboratory measurement, descriptive statistics will be provided for study baseline and all subsequent post-treatment scheduled visits. Changes from study baseline to the post-treatment visits will also be provided.

Changes in findings from study baseline physical examinations will be tabulated for each subject by examination category. If there are examination findings that change in more than one subject, these will be tabulated in a separate table and expressed as the number of subjects with the change out of the total. No statistics will be applied to the physical examination findings.

The SAP will provide additional details on the planned safety analyses.

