4.1 Safety Endpoints

4.1.1 Primary Safety Endpoint

The primary endpoint of the study is the incidence and frequency of AEs and SAEs assessed as related to Ace-ER over the duration of the study.

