Number of subjects with treatment-related TEAEs	xx (xx.x)	xx (xx.x)	xx (xx.x)	xx (xx.x)	xx (xx.x)	xx (xx.x)	xx (xx.x)	
Number of serious TEAEs	xx (xx.x)	xx (xx.x)	xx (xx.x)	xx (xx.x)	xx (xx.x)	xx (xx.x)	xx (xx.x)	
Number of subjects with serious TEAEs	xx (xx.x)	xx (xx.x)	xx (xx.x)	xx (xx.x)	xx (xx.x)	xx (xx.x)	xx (xx.x)	
Number of TEAEs causing discontinuation	xx	xx	xx	xx	xx	xx	xx	
Number of subjects with TEAEs causing discontinuation	xx (xx.x)	xx (xx.x)	xx (xx.x)	xx (xx.x)	xx (xx.x)	xx (xx.x)	xx (xx.x)

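### Adverse-event results are planned as crude percentages of all dosed subjects with no person-time measure, so they read low as 96-week incidence if follow-up is incomplete

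*SAP*

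**What the plan says.** SAP 4.1.1 defines the primary endpoint as "the incidence and frequency of AEs and SAEs assessed as related to Ace-ER over the duration of the study". SAP 8.7.1 turns this into a subject-level summary: "The number and proportion of subjects with any treatment-emergent adverse events (TEAEs"), broken down by system organ class, preferred term, severity, outcome and relationship.

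The denominator is fixed by SAP section 6: "The safety analysis set consists of all subjects who receive at least one dose of study drug in CL302". Length of follow-up plays no part in it.

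The overall TEAE template in SAP 10.7 shows former-placebo CL301, active CL301, all CL301, CL202, CL203 and Total side by side. Its row for related events is "Number of subjects with treatment-related TEAEs", given as n (%). It also has event-count rows for serious TEAEs and for TEAEs causing discontinuation. It has no event-count row for related TEAEs and no person-time row.

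Time on treatment is reported separately: SAP 8.5.1 says "the total treatment duration will be summarized for the Safety Analysis Set". No section links it to the adverse-event tables.

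Protocol 7.6.6 states: "The numbers (frequency) and incidence rates of AEs and SAEs will be summarized by treatment group". It does not define those rates, and SAP section 1 gives the SAP precedence on analysis methods.

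**The concern.** Time at risk can differ between subjects. Protocol 7.5.5.9 and 8.5.4.1 record adverse events until 30 days after each subject's own last dose. Subjects may withdraw or be removed, and Protocol 7.3.3 adds that "Ultragenyx also reserves the right to discontinue the study at any time for either clinical or administrative reasons". The SAP itself labels its analyses Week 96/ET.

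Someone who leaves event-free at week 20 adds one to the denominator, exactly like someone observed event-free for 96 weeks. Longer observation can only add first events, so the crude percentage can equal but never exceed what full follow-up of the same subjects would have shown.

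The stated purpose is long-term safety, and the events most affected are those that are spread over time or come late. Exposure adjustment is not foreign to the programme. On gastrointestinal events in the earlier controlled study, Protocol 5.2.4 says: "Exposure adjusted rates of these GI events were similar when comparing 6 g/day to placebo".

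**Working it through.** **The plan's own figure.** Protocol 7.6.1 gives 55 + 80 + 30 = 165, which reproduces. SAP 3.5 says about 180 with no split by cohort. Both are roll-over counts. No adverse-event rate, withdrawal rate or safety precision is stated, so there is no safety figure to reproduce.

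**Inputs.**
- Planned follow-up T = 96 weeks (SAP 3.2).
- True 96-week risk R: assumed, 30% for illustration.
- Share w withdrawing, at times spread evenly over 0 to 96 weeks and unrelated to event risk: assumed, 10% or 20%.
- Week of a sponsor stop: assumed, 48.

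**Constant hazard.**
- Cumulative hazard H = −ln(1 − R) = −ln(0.70) = 0.3567, or 0.003715 per week.
- Average risk seen in those who withdraw = 1 − R/H = 1 − 0.30/0.3567 = 0.1589.
- Crude proportion = (1 − w)R + w × 0.1589.
- w = 10%: 0.270 + 0.0159 = **28.6%**.
- w = 20%: 0.240 + 0.0318 = **27.2%**.
- All follow-up stopped at week 48: 1 − exp(−0.3567/2) = 1 − 0.8367 = **16.3%**.

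**Same calculation at other risks.**

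| True risk | 10% withdraw | 20% withdraw | Stop at week 48 |
|---|---|---|---|
| 5% | 4.75% | 4.50% | 2.5% |
| 20% | 19.0% | 18.1% | 10.6% |
| 50% | 47.8% | 45.6% | 29.3% |
| 90% | 87.1% | 84.2% | 68.4% |

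The relative loss from withdrawal is about 5% and 10% for risks up to 20%, and about 3% and 6% at a risk of 90%.

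**Range around the 30% case.**
- Largest loss under equal underlying risk, with every withdrawal immediate and event-free: 0.9 × 30 = 27.0% and 0.8 × 30 = 24.0%.
- All events in the first 24 weeks: hazard 0.3567/24 = 0.01486 per week. Average risk seen in those who withdraw = [24 − 0.30/0.01486 + 72 × 0.30]/96 = 0.265. The crude figures are 0.270 + 0.0265 = 29.6% and 0.240 + 0.0529 = 29.3%, and a stop at week 48 costs nothing.
- Complete follow-up: no loss.

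The model ignores the 30 days of collection after the last dose, which would shrink these losses slightly.

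**What a rate would show.** Under the constant hazard, the first-event rate is 0.003715 × 52 × 100 = 19.3 per 100 subject-years, whether follow-up is 48 or 96 weeks. Two cohorts with that same rate, one followed for 48 weeks and one for 96, would appear in the template as 16.3% and 30.0%.

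**The case against.** The SAP never calls its percentage a 96-week risk. The endpoint runs over the duration of the study, and n/N describes what was observed. Safety is descriptive (SAP 8.7), with no between-cohort test and no planned comparison with parent-study rates. All of this stands: the fault lies in reading the figure as long-term incidence, although that is the natural reading in a long-term safety study.

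The likely size may also be small. Protocol 5.2.3 has 46 + 13 = 59 subjects in CL202, and Protocol 7.6.1 expects 55 to roll over, a gap of 4/59 = 6.8%. (The SAP 10.7 footnote says 10 treatment-naïve subjects, which would make the gap 1/56 = 1.8%.) At 7% withdrawal, 30% reads 0.93 × 30 + 0.07 × 15.9 = 29.0%. The 1.4 and 2.8 points lost at 10% and 20% withdrawal are below one binomial standard error: √(0.3 × 0.7/N) is 3.6 points at N = 165, 5.1 at N = 80 and 8.4 at N = 30. This argues for modest priority. It does not remove a loss that runs in one direction only, and it does not cover a sponsor stop.

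Several stronger readings are tempting, and the documents do not support them:
- **Everyone who leaves early counts as event-free.** No. A TEAE before leaving, or within 30 days after the last dose, is in the numerator. Only those who leave event-free dilute the percentage.
- **Nothing but n (%) is planned.** No. Two kinds of event count are in the template, and treatment duration is summarised, so shortened exposure would be visible.
- **Withdrawal for poor tolerability lowers the percentage.** Usually not. Such a subject has normally had an event, is counted, and appears in the discontinuation rows.
- **The protocol commits to person-time rates.** Its term is undefined, and the SAP governs.

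**Conclusion.** The point holds as a limitation of the planned display. The primary safety result has no person-time measure. Read as 96-week incidence it is too low whenever follow-up is incomplete for event-free subjects, and columns with unequal follow-up are not comparable.

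Under a constant hazard and uniform withdrawal unrelated to risk, the loss on a true 30% is 1.4 to 2.8 points at 10% to 20% withdrawal. It is 13.7 points if all follow-up ended at week 48. It is near zero for early events and absent with complete follow-up. Withdrawal share, hazard shape and stop date are all assumptions. The documents give no withdrawal rate, and the sponsor stop is only a reserved right, so nobody should infer that a material bias has occurred or will occur.

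This is a cheap improvement worth making, not a reason to doubt the safety analysis as a whole.

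**What to change.** In SAP 8.7.1 and the 10.7 TEAE template, keep n (%) and add for each column:

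- total subject-years at risk, from first CL302 dose to the earlier of last dose plus 30 days or last contact;
- first-event incidence per 100 subject-years, with each subject's time ending at the first such event;
- event rate per 100 subject-years, counting all events over all time at risk;
- 95% confidence intervals for both rates.

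Do this for all TEAEs, related TEAEs, serious TEAEs, TEAEs causing discontinuation, and the gastrointestinal and liver groups of Appendix 10.6. The related-event row would also supply the frequency part of the primary endpoint, and the definition would give meaning to the undefined rates in Protocol 7.6.6.

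The cost is SAP wording and some extra table rows. Dosing dates and event dates are already needed for SAP 7.2.1, 7.2.3 and 8.5.1.

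State the limits in the SAP. A single rate assumes a roughly constant hazard. It does not remove differences in prior exposure (former placebo against previously treated) or in visit schedule (CL203 has no Month 2 or Month 4 visit). Cross-cohort statements should therefore remain descriptive.
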